7.2 STATISTICAL ANALYSIS PLAN

Data will be collected on electronic clinical records or paper CRFs which include the patients name, DOB and hospital number. Participants will be assigned a study number which will be noted on all records. Data will then be entered on to a password-protected computer database on the secure hospital IT system; only the study number will be used to identify the patient data.

De-identified data and all appropriate documentation will be stored for a minimum of 10 years after the completion of the study including the follow-up period.

The primary analysis will be performed on an intention-to-treat basis, irrespective of compliance and whether or not they have completed the prescribed regimen. A secondary analysis will also be performed on a per-protocol basis.

7.2.1 ANALYSIS OF PRIMARY ENDPOINT

The primary analysis will compare the proportion of participants experiencing adverse events classified as mild non-transient symptoms or more severe (see table 9) during CM-OIT (phase 2), in those who have received SLIT pretreatment (group S) compared to placebo (group C) using a two-sided Fisher's exact test at a $p<0.05$ level of significance.

²⁷ Wood. J Allergy Clin Immunol. 2013 March ; 131(3): 805–812

²⁸ Narisety et al. J Allergy Clin Immunol. 2015 May;135(5):1275-82.e1-6.

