4.3. WITHDRAWAL CRITERIA

Subjects will be free to withdraw from the study at any time without affecting their future medical care. Subjects who are withdrawn from active treatment will be invited to remain in the study for assessment of outcome relating to safety and HRQL measures (HRQL will be assessed 3 months after withdrawal).

The safety of study participants is paramount in this study: subjects who are assessed as having had anaphylaxis to a home dose but who do not receive IM adrenaline as per the management plan will have further updosing suspended until the family undergo retraining on the recognition and management of allergic symptoms.

A participant will be withdrawn from the study under the following circumstances:

- If, in the opinion of the study team, compliance with study procedures is suboptimal such that it compromises the patient's safety.
- If, in the opinion of the study team, further participation would adversely affect the participant's health.
- A child develops an exclusion criteria during the updosing phase of the study e.g. a new medication (which would normally be a contra-indication) is commenced.
- If consent is withdrawn or the subject fails to return for a study visit without due reason.

Any subject excluded from further participation will not be replaced, unless withdrawal occurs after initial DBPCFC but prior to allocation to treatment.

⁹Papadopoulos NG, Arakawa H, Carlsen KH, et al. International consensus on (ICON) pediatric asthma. *Allergy*. 2012;67:976-97.

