5.3.1 TREATMENT ALLOCATION

[figure not shown]
OIT outcomes are affected by a range of variables, including age, allergen-specific IgE to CM, threshold and the presence of asthma. It is therefore essential to maintain balance between treatment groups with respect to these predictors. However, stratified randomisation using several variables is not effective in small trials. Minimisation is a valid alternative to ordinary randomisation, and has the advantage that there will be only minor differences between groups in baseline variables which are used in the allocation process.¹³ With minimisation, the treatment allocated to the next participant enrolled in the trial depends on the characteristics of those participants already enrolled, with an element of weighted randomisation – typically 80% chance – of each participant getting the allocation that minimises any imbalance.

Participants will therefore be allocated using an online minimisation/randomization tool, Minim, with a random element using a weighting probability of 0.8, stratified by centre. Baseline variables included in the minimisation will be:

- age (under 12yrs, 13+yrs)
- sex
- specific IgE to CM (<30 kU/l, \geq 30 kU/l)³
- eliciting dose at DBPCFC (\leq 44mg, 144-444mg, $>$ 444mg CM protein; these cut-offs are based on published population-based dose distributions in CM-allergic children)
- documented tolerance to CM in baked foods (tolerant or allergic/unknown).
- asthma (none, no regular inhaled corticosteroid (equivalent to BST Step 1), regular ICS (equivalent to BTS Step 2 or above).

Group allocation (active vs placebo) will be concealed throughout the study until completion of the 2nd visit of the exit DBPCFC at 12 months.

The schema for treatment allocation will be as follows:

¹³ Altman DG, Bland JM. Treatment allocation by minimisation. BMJ. 2005 Apr 9; 330(7495): 843.

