7. STATISTICS AND DATA ANALYSIS

7.1 SAMPLE SIZE ESTIMATION

The primary objective of the study is to assess the impact of a 6 month SLIT pretreatment phase on the safety of conventional OIT in children with persistent cow's milk allergy. The primary outcome is the proportion of participants experiencing adverse events classified as mild non-transient symptoms or more severe (see table 9) during CM-OIT (phase 2), in those who have received SLIT pretreatment (group S) compared to placebo (group C). As a secondary outcome, we will assess whether any effect of SLIT is dependent on the sublingual route, by including a third treatment group who have the same dosing regimen as the SLIT group but take the dose orally, omitting the sublingual phase (group O).

The expected natural resolution rate in CM allergic children beyond preschool age is less than 10% in a 6 months period.²⁷ Up to 70% of children undergoing conventional OIT for CM allergy experience mild, transient symptoms e.g. oropharyngeal itch [20.23.38]. A previous study in 9 peanut-allergic subjects showed a 75% relative reduction in mild non-transient symptoms (or symptoms of greater severity) during OIT as a result of the SLIT pretreatment.²⁸ Assuming 10% loss-to-follow-up, we calculate that a sample size of 66 participants (allocated 1:1:1 to the treatment groups) will detect a difference in the rate of children experiencing mild, non-transient symptoms from 70% in the OIT-alone group to 18% in the group undergoing SLIT pre-treatment prior to OIT (i.e. a 75% reduction), with 80% power at a significance level of $p<0.01666$ (Bonferroni correction) to allow for three pairwise comparisons (to ensure the overall risk of type I error is under 5%).

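### The primary S vs C test, an unadjusted Fisher's exact test, is valid but conservative at 19-22 children per arm; Boschloo's test recovers a modest amount of power within the same nominal alpha

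*Combined protocol and SAP*

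**What the plan says.** Section 7.2.1 sets the primary analysis as a comparison of two proportions between those who "received SLIT pretreatment (group S) compared to placebo (group C) using a two-sided Fisher's exact test" at the 0.05 level. It names no covariate and no stratification.

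Allocation is more elaborate. Section 5.3.1 says "OIT outcomes are affected by a range of variables, including age, allergen-specific IgE to CM, threshold and the presence of asthma", and minimises on six baseline variables "with a random element using a weighting probability of 0.8, stratified by centre".

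The only regression for adverse events is the logistic model in section 7.2.2. It examines the influence of age, gender, asthma status, previous anaphylaxis and other unnamed factors. The text does not say whether treatment group is a term, so an adjusted S vs C comparison is left unspecified.

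On numbers, section 7.1 plans 66 children at 1:1:1, so 22 per arm, with 10% loss. Section 4.3 says "Any subject excluded from further participation will not be replaced" (apart from withdrawals before allocation). It also says that children taken off active treatment "will be invited to remain in the study for assessment of outcome relating to safety and HRQL measures". Section 7.2 adds "The primary analysis will be performed on an intention-to-treat basis, irrespective of compliance".

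**The concern.** Fisher's test conditions on the total number of events. With about 20 children per arm the set of attainable p-values is coarse, so the test rejects much less often than its nominal level allows. Part of the permitted type I error goes unused, and power is lost with it.

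That matters most if the true effect is smaller than planned. Section 7.1 bases the effect on very little: "A previous study in 9 peanut-allergic subjects showed a 75% relative reduction in mild non-transient symptoms". The trial is small and cannot easily recruit its way out of a lost margin.

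The planned test also makes no use of centre or of the variables that the protocol itself treats as prognostic.

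**Working it through.** **Inputs.** Arm size 22; loss 10%; risks 70% (C) and 18% (S); alpha 0.01666 in section 7.1 and 0.05 in section 7.2.1. Evaluable numbers: 22 × 0.90 = 19.8, and up to 22 if children who stop treatment stay for safety follow-up. All 16 splits from 19 to 22 per arm were therefore examined.

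**The plan's own figure.** A 75% reduction from 70% is 0.70 × 0.25 = 17.5%, rounded in the plan to 18%. Exact Fisher power at 20/20 and alpha 0.01666 is 78.5% with 17.5% and 77.2% with 18%. At 19 and 20 per arm with 18% it is 79.5-80.6%. The stated 80% is reproduced to within about 3 points.

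**Formulas.** For x events among n_S and y among n_C:
- Fisher rejects on R = {(x, y): two-sided p_F < alpha}.
- True size at common risk π = Σ over R of Bin(x; n_S, π) · Bin(y; n_C, π), maximised over π from 0.05% to 99.95%.
- Power = the same sum with risks 0.18 and 0.70.
- Boschloo rejects when p_F ≤ c, where c is the largest cut-off that keeps maximum size at or below alpha.

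**Results at alpha 0.05 (%), selected splits, Fisher / Boschloo.**

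| S/C | Maximum size | Power, 70 vs 18 | Power, 70 vs 35 |
|---|---|---|---|
| 19/19 | 2.8 / 4.5 | 88.7 / 90.7 | 49.4 / 53.5 |
| 20/20 | 2.5 / 4.6 | 88.4 / 92.7 | 46.8 / 57.8 |
| 19/21 | 3.4 / 4.8 | 90.4 / 94.2 | 49.1 / 59.8 |
| 21/21 | 2.3 / 4.8 | 89.7 / 94.4 | 49.2 / 61.9 |
| 21/22 | 3.6 / 4.7 | 93.0 / 94.4 | 58.0 / 60.4 |
| 22/22 | 2.4 / 5.0 | 91.9 / 95.7 | 53.5 / 65.7 |

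Over all 16 splits:
- Maximum size is 2.3-3.6% for Fisher (2.3-2.8% at equal arms, 3.2-3.6% at unequal arms) and 4.2-5.0% for Boschloo.
- At 70% vs 18% Fisher power is 88.4-93.5%, and Boschloo adds 1.1-4.7 points.
- At 70% vs 35% Boschloo adds 2.4-12.7 points.
- Boschloo's rejection region contains Fisher's at every split.

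**Averaged over independent 10% loss from 22 per arm, alpha 0.05.** Fisher / Boschloo power is 90.2 / 92.7% at 70 vs 18 (gain 2.5), 76.9 / 81.5% at 70 vs 25 (gain 4.6) and 51.8 / 58.1% at 70 vs 35 (gain 6.3). The 25% and 35% risks are illustrations.

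**At alpha 0.01666, 70% vs 18%.** The gain runs from 0.0 points (20/22) to 10.4 (19/19: 72.2% to 82.6%). At 20/20 power goes from 77.2% to 86.1%.

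**Minimisation and adjustment.** The exact figures treat the arms as independent binomials. A simulation of three-arm minimisation was also run: 66 children, weight 0.8 within centre, 10% random loss, 6,000 runs per scenario. The imbalance measure, factor prevalences and prognostic effects were assumed, because the documents do not give them. Across 16 null scenarios, size at nominal 5% was 1.6-3.2% for Fisher and 2.3-4.5% for Boschloo. Firth logistic regression on centre, eliciting-dose category and IgE gave -0.4 to +3.5 points of power relative to Boschloo at 70% vs 18%, and 0.0 to +12.6 at 70% vs 35%. The high ends need strong assumed effects.

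**The case against.** The strongest reply is that this is a preference. Fisher's test is prespecified, two-sided and valid, and at the 0.05 of section 7.2.1 it exceeds the 80% target at every split. The largest gains (4.7 and 12.7 points) both occur at 21/21, whereas evaluable arms were equal in only about 15-16% of simulated trials. Over the 12 unequal splits the gain is 1.1-4.0 points (mean 2.3) at the planned effect and 2.4-10.7 (mean 6.0) at 70% vs 35%. Even with Boschloo, loss-averaged power at 70% vs 35% is only 58.1%, so it would not rescue the trial. An adjusted model that leaves out age and asthma also sits awkwardly with a complaint that prognostic variables are ignored.

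Most of this stands as a limit on size. The typical gain at the planned effect is small, and the adjusted analysis should be supportive and short. About 20 × 0.70 + 20 × 0.18 = 17.6 events among 40 children will not carry many terms, so leaving out age and asthma is a judgement made for parsimony.

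What does not stand is that nothing is gained. At the same nominal alpha, with the ordering named above, Boschloo rejects whenever Fisher does and sometimes when Fisher does not, so it cannot lose power. The gain is not free of type I error: actual maximum size rises to 4.2-5.0%. It stays within the nominal level.

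**Conclusion.** The point holds as an efficiency improvement worth making. At alpha 0.05 the cost of Fisher's test at the planned effect is about 2.5 points on average (1.1-4.7 by split), from a base near 90%. It is larger for smaller effects. The figures rest on independent binomial arms of 19-22 and, for the average, on independent 10% loss.

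Stronger readings that a reader might infer, and that the documents do not support:
- *The primary test is wrong or biased.* Its size never exceeds 5%.
- *Ignoring the minimisation variables inflates false positives.* In the simulations, which rest on assumed inputs, size stayed below nominal.
- *The choice of Fisher leaves the trial underpowered.* At 0.05 and the planned risks it does not. Power falls below 80% at some splits only under 0.01666. Which alpha governs is a separate question, on which sections 7.1 and 7.2.1 disagree.
- *Section 7.2.2 rules out an adjusted treatment comparison.* It leaves the model terms open.
- *Adjustment would bring a known gain.* Its size cannot be derived from the documents.

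**What to change.** Amend section 7.2.1 before any allocation is unblinded for analysis, and state that time point explicitly, because the concealment rule in section 5.3.1 could be read as ending participant by participant.

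1. **Primary test.** Use Boschloo's unconditional exact test of S vs C at the same two-sided alpha, with the two-sided Fisher p-value as the ordering statistic. Keep Fisher's test as a sensitivity analysis.
2. **One supportive analysis.** Compare S with C adjusted for centre, eliciting-dose category and milk-specific IgE (<30 / ≥30 kU/l), for example by Firth-penalised logistic regression with a penalised likelihood-ratio p-value.
3. **Decision rule.** State that the Boschloo p-value decides if the analyses disagree.

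The cost is SAP wording, although it does replace the named primary test. No extra children, visits or data are needed. The downsides are less familiar software and the need to name the version: some packages double a one-sided Boschloo test, whose rejection region fails to contain Fisher's at 10 of the 64 splits from 15 to 22 per arm at 5%. The supportive model also carries mild model dependence.

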7.2.2 ANALYSIS OF SECONDARY ENDPOINTS

The following secondary analyses will be performed using two-sided testing for non-parametric data at a $p<0.05$ level of significance:

- The incidence of adverse events experienced (including rate of withdrawals, and anaphylaxis/adrenaline use during updosing) between groups S, O and C in phases 1 and 2. Statistical differences will be determined using Fisher's exact test for proportions or using non-parametric tests for graded reactions. Logistic regression will be used to assess the influence of age, gender, asthma status and prior history of anaphylaxis amongst other factors on the incidence of adverse events.
- Efficacy defined at DBPCFC as the proportion of study participants experiencing:
 - No symptoms (or only mild transient symptoms as per table 9) to 8 grams CM protein (approx. 250mls fresh milk) ("Complete desensitisation")
 - No symptoms (or only mild transient symptoms as per table 9) to at least 1.4 grams CM protein (approx. 45mls fresh milk) ("Partial desensitisation")
 - At least a 10-fold increase in eliciting dose (defined as the lowest dose which elicits objective symptoms or signs at challenge)....at 6 and 12 months in the different treatment groups, using a two-sided Fisher's exact test at a $p<0.05$ level of significance.
- This will include a comparison of the efficacy of SLIT compared to the same dose administered orally without a sublingual phase (to address hypothesis 2), and its effect on the subsequent safety of OIT.
 - Immunological outcomes (titrated skin prick test, serum IgE) at baseline, 6 and 12 months.
 - Change in health-related quality of life (HRQL) measures at 6, 12 and 15 months, as assessed by validated questionnaires (FAQLQ, FAIM, EQ-5D) in study participants and their parents.
- Change in health-related quality of life (HRQL) measures at 6, 12 and 15 months, as assessed by validated questionnaires (FAQLQ, FAIM, EQ-5D) in study participants and their parents.
- Immunological outcomes (titrated skin prick test, serum IgE) at baseline, 6 and 12 months.
- The trend in CM-peptide binding over time as well as the potential influence of baseline peptide binding on the outcome of CM-IT will be assessed using a bioinformatics approach as in previous studies.²⁹

Secondary analyses will include a comparison of the safety/efficacy of SLIT compared to the same dose administered orally without a sublingual phase (to address hypothesis 2), and its effect on the subsequent safety/efficacy of OIT.

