5.8.2 QUALITY OF LIFE ASSESSMENTS

The impact of OIT on participants' health-related quality of life (HRQL) will be assessed both from parents' and participants' perspective using abbreviated versions of disease-specific validated "food-allergy quality of life questionnaire" (FAQL-Q) in its parental,¹⁵ child¹⁶ and teenage¹⁷ forms at five time points during the study:

- i. baseline, at screening
- ii. baseline, after completion of the baseline DBPCFC
- iii. prior to the DBPCFC in between Phase 1 and Phase 2, at around 6 months
- iv. prior to the exit DBPCFC after Phase 2.
- v. 3 months after the exit DBPCFC (15 months visit).

These new abbreviated versions have been validated (data submitted for publication). We will also assess the impact of the child's food allergy on parent QoL using the FAQL-Parent Burden form (which has been validated in a UK population).¹⁸

The FAQL-questionnaires are based on a 7-point Likert scale and changes greater than 0.5 points over time have been defined as clinically significant.¹⁹ Previous studies have reported a positive effect on QoL following OIT to CM from the parents' perspective.²⁰ However, there are no controlled studies which have addressed the impact on QoL as perceived by the participants themselves. This is a significant knowledge gap, since there is a concern that while parents report an improved HRQL when their child undergoes immunotherapy the child themselves may experience a worsening of HRQL measures due to frequent side effects and need to alter their activities following immunotherapy doses.

In line with current expert opinion, and to ensure the ability to compare responses consistently during the 12 months of OIT, children who are age 12 at study commencement will be asked to complete the Teenage versions of the QoL assessments unless there are difficulties with comprehension which preclude this.

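### HRQL and immunological comparisons between arms have no baseline covariate, which loses precision at about 20 evaluable children per arm

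*Combined protocol and SAP*

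**What the plan says.** Section 7.2.2 opens its list of secondary analyses with "The following secondary analyses will be performed using two-sided testing for non-parametric data", at the 0.05 level. Two of the items under that sentence are "Change in health-related quality of life (HRQL) measures at 6, 12 and 15 months" and "Immunological outcomes (titrated skin prick test, serum IgE) at baseline, 6 and 12 months". Neither item names a specific test, a covariate, an effect estimate or a confidence interval. HRQL is framed as change; the immunological outcomes are listed by time point only. The one covariate model in section 7.2 is for adverse events: "Logistic regression will be used to assess the influence of age, gender, asthma status and prior history of anaphylaxis", among other factors.

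Pre-treatment values exist. Section 5.8.2 schedules HRQL twice before treatment, "baseline, at screening" and "baseline, after completion of the baseline DBPCFC". Section 5.8.1 schedules skin tests at screening, 6 and 12 months, and section 5.8.3 schedules bloods at baseline, 6 and 12 months. Section 5.8.2 also says of the FAQL questionnaires that "changes greater than 0.5 points over time have been defined as clinically significant". Section 7.2.2 does not say from which of the two HRQL baselines change is measured.

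**The concern.** The effect of immunotherapy on HRQL is a stated secondary objective (section 2.2), and section 5.8.2 calls for evidence from the children themselves. With arms this small, an analysis that leaves out the baseline value gives wider intervals than the same data could support.

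Chance imbalance also matters. Section 5.3.1 minimises on age, sex, specific IgE split at 30 kU/l, eliciting dose, baked-milk tolerance and asthma, stratified by centre. HRQL scores and skin-test size are not on that list, and IgE is balanced only above and below one cut-off.

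**Working it through.** **Arm size.** Section 7.1 gives 66 children allocated 1:1:1 and 10% loss: 66/3 = 22, and 22 × 0.9 = 19.8 evaluable per arm. That size was set for the primary endpoint (70% v 18%, alpha 0.01666, 80% power). At 20 per arm the exact power of Fisher's test is 77.2% for 18%, and 78.5% for 17.5% (exactly a 75% reduction), so the plan's figure is approximately reproduced. The documents give no sample size or power for HRQL or immunology.

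**Variance.** Let r be the correlation between baseline and follow-up, with equal variances. The variance of the difference between two arms of n is (2σ²/n) × v, where:

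- follow-up value alone: v = 1
- change score: v = 2(1 − r)
- analysis of covariance: v = 1 − r²

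So covariance/change = (1 − r²)/(2(1 − r)) = (1 + r)/2, and covariance/follow-up = 1 − r². The documents give no r, so it is varied:

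| Assumed r | Ratio to change score | Reduction | 20 per arm works like | Ratio to follow-up value | Reduction | 20 per arm works like |
|---|---|---|---|---|---|---|
| 0.3 | 0.65 | 35% | 30.8 | 0.91 | 9% | 22.0 |
| 0.5 | 0.75 | 25% | 26.7 | 0.75 | 25% | 26.7 |
| 0.7 | 0.85 | 15% | 23.5 | 0.51 | 49% | 39.2 |
| 0.8 | 0.90 | 10% | 22.2 | 0.36 | 64% | 55.6 |

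Each equivalent size is 20 divided by the ratio. The change-score columns fit HRQL as section 7.2.2 words it. The follow-up columns apply if immunological outcomes are compared at each time point without subtracting baseline, which the wording would allow.

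**Check against a rank test.** The formula compares means and ignores the small cost of estimating the slope. A simulation covers both points (normal data, 20 per arm, 4,000 runs, true difference 0.5 SD, two-sided 0.05):

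| Assumed r | Mann-Whitney on change | Analysis of covariance |
|---|---|---|
| 0.3 | 24% | 35% |
| 0.5 | 33% | 41% |
| 0.7 | 48% | 57% |
| 0.8 | 65% | 71% |

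Mann-Whitney on the follow-up value alone had 31% to 32% power throughout. With no true difference, all three methods rejected in 4.4% to 5.8% of runs. Most of the loss comes from the missing covariate, since the rank test keeps about 95% efficiency on normal data.

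**Chance imbalance.** The standard error of a baseline difference between two arms of 20 is √(2/20) = 0.316 SD. Given an observed gap of that size, a change-score contrast is shifted by (1 − r) × 0.316 SD, in favour of the arm that started worse. At r = 0.5 that is 0.158 SD. Over repeated randomisations the shift averages to zero.

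**The case against.** Several objections stand and limit the point.

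- The plan omits adjustment; it does not rule it out. The defect is under-specification. An adjusted model chosen after the data are seen would, however, be post hoc.
- A reader might infer that change scores bias the HRQL comparison through regression to the mean. The documents do not support that: allocation is randomised, so regression to the mean is equal across arms in expectation.
- A reader might infer that a rank test leaves no effect size. It does not: a Hodges-Lehmann shift with a confidence interval is available, though section 7.2.2 does not plan one.
- A reader might infer that the plan compares changes in skin tests and IgE. Sections 3.1.2 and 7.2.2 list those outcomes by time point. Section 5.8.3 mentions antibody changes, but among the mechanistic assessments.
- The 0.5-point figure concerns change over time on the FAQL questionnaires. It is not a margin between arms and does not apply to EQ-5D, IgE or skin tests.
- Part of the HRQL objective is a before-and-after question in all children (section 3), where this gain does not arise.
- The gain over a change score shrinks as r rises, to (1 + 0.9)/2 = 0.95, or 5%, at r = 0.9.
- Ranks are a defensible choice for skewed or ordinal data. Titrated skin tests are read on six concentrations (section 5.8.1), which a linear model does not suit.
- IgE imbalance is already partly controlled through minimisation.

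None of this removes the gain in precision for comparisons between arms.

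**Conclusion.** The point holds as one of efficiency in secondary endpoints; the primary result is untouched. For arm contrasts at about 20 children per arm, adjusting for baseline would cut variance by 10% to 35% against a change score. Against an unadjusted follow-up value the cut would be 9% to 64%. In the simulation, power at a 0.5 SD difference rose by 6 to 11 percentage points over a Mann-Whitney test on change. These figures rest on an assumed r of 0.3 to 0.8, equal variances and, for the simulation, normal data; the documents supply none of these. Adjustment would also deal with chance imbalance in HRQL and skin-test size. The documents do not support reading the plan as biased, as unable to yield an effect size, or as deciding against adjustment.

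**What to change.** In section 7.2.2, for the S-C and S-O comparisons:

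- Analyse each HRQL score (6, 12 and 15 months) and log-transformed specific IgE (6 and 12 months) by a linear model of the follow-up value on arm, baseline value and centre, optionally with the other minimisation factors. Report each difference with a 95% confidence interval.
- Use rank-based analysis of covariance for the titrated skin-test endpoint.
- Keep the planned rank tests as sensitivity analyses.
- Name the screening HRQL score as the baseline. Like the 6- and 12-month scores, it is taken before a challenge. That reason does not extend to 15 months, which follows the exit challenge, but one named baseline still removes the choice.
- Report within-arm FAQLQ change separately against the 0.5-point threshold.
- Confirm that FAIM has a baseline, since section 5.8.2 gives it no schedule of its own.

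The cost is SAP wording: no extra children, visits or samples. The small downside is a model assumption, which the rank-test sensitivity analysis covers.
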